7 BASELINE DATA AND FLOW CHART

7.1 Presentation of Baseline Data

The following baseline data will be presented by site and vaccination group: age, gender, gestational age, day care attendance, number of children living in the home, insurance payer status, ethnicity, race, receipt of first dose of influenza vaccine, receipt of inactivated influenza vaccine at Visit 1, and receipt of live vaccines at Visit 1. Summary statistics (e.g., mean, median, standard deviation, interquartile range) will be presented for continuous variables. Categorical variables will be described with frequencies and percentages.

7.2 Flow Chart

The number of enrolled participants will be presented in a flow chart by site and vaccination group. The number of visits completed and missed will be presented, along with a breakdown of the two analysis populations.

8 ANALYSIS OF STUDY OBJECTIVES

8.1 Primary Objective

The primary objective (PO 1) of the study is to compare the proportion of children with fever (temperature $\geq 38.0^{\circ}\text{C}$ or $\geq 100.4^{\circ}\text{F}$) on day 1 and/or day 2 following Visit 1 and/or Visit 2. This information is captured on the memory aid form which is captured in the REDCap database. Fever on day 1 and/or day 2 after either visit will be counted as positive (1) for this analysis and no fever reported will be negative (0). The proportions will be compared between the simultaneous versus the sequential group using a Mantel-Haenszel statistic in a stratified analysis by site to control for the randomization blocks at the two-sided alpha 0.05 level. The relative risk and corresponding 95% confidence interval for the occurrence fever will also be calculated.

8.2 Secondary Objectives

There are two secondary objectives for this study.

- a) The first secondary objective (SO 1) is to compare the proportions of children with fever on day 1 and/or day 2 after Visit 1 and Visit 2 separately, in the simultaneous versus sequential vaccination group. Fever on day 1 and/or day 2 after either visit will be counted as positive (1) for this analysis and no fever reported will be negative (0). Proportions at each visit will be compared between the simultaneous and the sequential vaccination groups using a Mantel-Haenszel statistic in a stratified analysis by site to control for the randomization blocks. The relative risk and corresponding 95% confidence interval for the occurrence of any fever on day 1 and/or day 2 after Visit 1 and Visit 2 separately will also be calculated. There are two separate statistical tests being performed at the alpha 0.05 level.
- b) The secondary objective (SO 2) is to compare the clinical importance of fever on day 1 and/or day 2 after Visit 1 and Visit 2 (separately and combined) in the simultaneous versus sequential group. Clinical importance is assessed based on severity of fever, duration of fever, and medical care utilization for fever. This information is captured on the memory aid form in the REDCap database.
 1. Severity of fever: To evaluate the severity of fever, we will present the proportions of children with the highest level of fever defined as Grade 2 and/or 3 ($\geq 38.6^{\circ}\text{C}$) on day 1 or day 2 following Visit 1, Visit 2 and Visit 1 and 2 combined by simultaneous and sequential vaccination groups.
 2. Duration of fever: To evaluate the duration of fever, the following analysis will be performed: The mean duration of any fever (in days) will be compared by simultaneous and sequential vaccination groups for children with fever that began on days 1 or 2 following Visit 1, Visit 2 and Visit 1 and 2 combined. Each consecutive day of fever on the memory aid will be counted per child per visit. Thus, a child could contribute a maximum of 8 days per study visit, should a fever be reported at each day on the memory aid. A child having fever on day 1, no fever on day 2, and fever on day 3 only has 1 day of fever.
 3. Medical care utilization for fever: We will present and compare the proportion of children with medical care utilization for fever (telephone contact, medical

office visit, emergency department visit or hospital admission) on day 1 and/or day 2 following Visit 1, Visit 2 and Visit 1 and 2 combined. Medical utilization for fever will be counted as positive for this analysis if onset of fever on day 1 and/or day 2 plus medical utilization on day 1, day 2 or day 3 after fever. Medical care related to fever will be determined by report on the diary.

Proportions will be compared between the simultaneous and the sequential vaccination groups using a Mantel-Haenszal statistic (three tests) in a stratified analysis by site to control for the randomization blocks. The duration of fever will be compared between groups using a Mann-Whitney U/Wilcoxon rank-sum test (three tests).

No adjustments will be made to the alpha level (two-sided alpha=0.05) for these secondary objectives.

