2.1 Study Outcome Measures as Related to Objectives**Primary Outcome Measure (POM):**

POM 1.1: Proportion of children with fever (temperature $\geq 38.0^{\circ}\text{C}$ or $\geq 100.4^{\circ}\text{F}$) on day 1 and/or day 2 following Visit 1 and/or Visit 2.

Secondary Outcome Measures (SOM):

SOM 1.1: Proportion of children with fever (temperature $\geq 38.0^{\circ}\text{C}$ or $\geq 100.4^{\circ}\text{F}$) on day 1 and/or day 2 following Visit 1.

SOM 1.2: Proportion of children with fever (temperature $\geq 38.0^{\circ}\text{C}$ or $\geq 100.4^{\circ}\text{F}$) on day 1 and/or day 2 following Visit 2

SOM 2.1: Proportions of children with moderate/severe fever (GRADE 2 and/or 3) on day 1 and/or day 2 following Visit 1, Visit 2, and Visit 1 and Visit 2 combined.

SOM 2.2: Average number of consecutive days of fever (temperature $\geq 38.0^{\circ}$ C or $\geq 100.4^{\circ}$ F) per subject for fever starting on day 1 or 2 following Visit 1, Visit 2 and Visit 1 and Visit 2 combined.

Note: fever starting on day 1 or 2 could continue through day 8.

SOM 2.3: Proportion of children with medical care utilization (telephone call, medical office visit, emergency department visit, or hospital admission) for fever on day 1 and/or day 2 following Visit 1, Visit 2 and Visit 1 and Visit 2 combined.

Exploratory Outcome Measures (EOM):

EOM 1.1: Average peak temperature of children with fever (temperature $\geq 38.0^{\circ}$ C or $\geq 100.4^{\circ}$ F) on day 1 and/or day 2 following Visit 1, Visit 2, and Visit 1 and Visit 2 combined.

EOM 1.2: Total number of fever degree-days (temperature $\geq 38.0^{\circ}$ C or $\geq 100.4^{\circ}$ F) on day 1 and/or day 2 per subject following Visit 1, Visit 2, and Visit 1 and Visit 2 combined.

EOM 2.1: Proportion of children with antipyretic use for fever on day 1 and/or day 2 following Visit 1, Visit 2 and Visit 1 and Visit 2 combined.

EOM 3.1: Proportions of children with fever at different levels of severity (Grades 1, 2, and 3) on day 1 and/or day 2 following Visit 1 and Visit 2

EOM 3.2: Proportions of children with fever at different levels of severity (Grades 1, 2, and 3) on days 3-8 following Visit 1 and Visit 2

EOM 3.3: The proportion of children with fever at different levels of severity (Grades 1, 2,3 and all Grade) on days 1-8 following Visit 1 and Visit 2

EOM 4.1: Proportion of children with fever (temperature $\geq 38.0^{\circ}$ C or $\geq 100.4^{\circ}$ F) on at least one day on day 3-8 following Visit 1.

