6.2 Analysis Plan

- 6.2.1 Study Populations** – There will be two study populations, the Intent-to-Treat (ITT) and Per Protocol populations. The ITT Population includes any participant that was enrolled, randomized into the study, and received at least one study vaccine at Visit 1. The Per Protocol Population is a subset of the ITT Population excluding those participants who do not provide valid temperature data on days 1 and 2 following Visit 1 and Visit 2 and those with major protocol violations as determined by the study investigators. Statistical analyses will be performed for both study populations, or the ITT Population only if no participants are excluded from the Per Protocol Population.
- 6.2.2 Primary Objective 1** – To compare the proportions of children with fever following simultaneous versus sequential vaccination with PCV13, DTaP, and IIV during 2 visits. Children in the sequential vaccination group will receive PCV13 and DTaP at Visit 1 followed by IIV and health education at Visit 2. Children in the simultaneous vaccination group will receive PCV13, DTaP, and IIV at Visit 1, followed by a health education visit without vaccination at Visit 2. Fever will be assessed on the visit day of, and the day after (days 1-2) each visit.

Temperatures will be measured in children on the evening of, and for 7 subsequent evenings following Visit 1 and Visit 2. For the primary objective we will compare the proportions of children with fever (Temperature $\geq 38.0^{\circ}\text{C}$ or $\geq 100.4^{\circ}\text{F}$) on day 1 and/or day 2 following Visit 1 and Visit 2 between the simultaneous and the sequential vaccination groups. Fever on day 1 and/or day 2 after either visit will be counted as positive for this analysis. The proportions will be compared using a Mantel-Haenszel statistic in a stratified analysis by site to control for the randomization blocks at the two-sided alpha 0.05 level. The relative risk and corresponding 95% confidence interval for the occurrence fever will also be calculated.

- 6.2.3 Secondary Objective 1** – To compare the proportions of children with fever on day 1 and/or day 2 after Visit 1 and Visit 2 separately, in the simultaneous versus sequential vaccination group.

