For this secondary objective we will present the proportions of children with any fever on day 1 and/or day 2 following vaccination for Visit 1 and separately for Visit 2. Fever on day 1 and/or day 2 after either visit will be counted as positive for this analysis. Proportions at each visit will be compared between the simultaneous and the sequential vaccination groups using a Mantel-Haenszel statistic in a stratified analysis by site to control for the randomization blocks. The relative risk and corresponding 95% confidence interval for the occurrence of any fever on day 1 and/or day 2 after Visit 1 and/or Visit 2 will also be calculated.

6.2.4 Secondary Objective 2 – To compare the clinical importance of fever on day 1 and/or day 2 after Visit 1 and Visit 2 (separately and combined) in the simultaneous versus sequential group. Clinical importance is assessed based on severity of fever, duration of fever, and medical care utilization for fever.

To evaluate the severity of fever, we will present the proportions of children with the highest level of fever defined as Grade 2 and/or 3 ($\geq 38.6^{\circ}\text{C}$ and/or $\geq 39.6^{\circ}\text{C}$) on day 1 or day 2 following Visit 1, Visit 2 and Visit 1 and 2 combined by simultaneous and sequential vaccination groups.

To evaluate the duration of fever, the following analysis will be performed: The mean duration of any fever (in days) will be compared by simultaneous and sequential vaccination groups for children with fever that began on days 1 or 2 following Visit 1, Visit 2 and Visit 1 and 2 combined. Each consecutive day of fever on the memory aid will be counted per child per visit. Thus, a child could contribute a maximum of 8 days per study visit, should a fever be reported at each day on the memory aid.

Furthermore, we will present and compare the proportion of children with medical care utilization for fever (telephone contact, medical office visit, emergency department visit or hospital admission) on day 1 and/or day 2 following Visit 1, Visit 2 and Visit 1 and 2 combined.

Proportions will be compared between the simultaneous and the sequential vaccination groups using a Mantel-Haenszel statistic in a stratified analysis by center to control for the randomization blocks. The duration of fever will be compared between groups using a Mann-Whitney U/Wilcoxon rank-sum test. No adjustments will be made to the alpha level (two-sided $\alpha=0.05$) for these secondary objectives.

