3.2 Secondary

- a)
 - 1. SOM 1.1: Proportion of children with fever (temperature $\geq 38.0^{\circ}\text{C}$ or $\geq 100.4^{\circ}\text{F}$) on day 1 and/or day 2 following Visit 1.
 - 2. SOM 1.2: Proportion of children with fever (temperature $\geq 38.0^{\circ}\text{C}$ or $\geq 100.4^{\circ}\text{F}$) on day 1 and/or day 2 following Visit 2.
- b)
 - 1. SOM 2.1: Proportions of children with moderate/severe fever (GRADE 2 and/or 3) on day 1 and/or day 2 following Visit 1, Visit 2, and Visit 1 and Visit 2 combined.
 - 2. SOM 2.2: Average number of consecutive days of fever (temperature $\geq 38.0^{\circ}\text{C}$ or $\geq 100.4^{\circ}\text{F}$) per subject for fever starting on day 1 or 2 following Visit 1, Visit 2 and Visit 1 and Visit 2 combined. Note: fever starting on day 1 or 2 could continue through day 8.
 - 3. SOM 2.3: Proportion of children with medical care utilization (telephone call, medical office visit, emergency department visit, or hospital admission) for fever on day 1 and/or day 2 following Visit 1, Visit 2 and Visit 1 and Visit 2 combined.

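### Does the coding sentence for Secondary Objective 1 turn the two per-visit fever endpoints into a repeat of the primary endpoint?

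*Combined protocol and SAP*

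**What the plan says.** Protocol 2.1 and SAP 3.2 give SO 1 two outcome measures, each confined to days 1-2 after one visit: SOM 1.1 ("SOM 1.1: Proportion of children with fever" after Visit 1) and SOM 1.2 (the same after Visit 2). The primary measure, POM 1.1, is the union: fever in that window after Visit 1, Visit 2 or both.

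For SO 1, SAP 8.2 a) contains these elements:

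- the objective, which is to compare fever after the two visits separately;
- the coding sentence, "Fever on day 1 and/or day 2 after either visit will be counted as positive (1) for this analysis";
- a site-stratified Mantel-Haenszel comparison of the proportions visit by visit;
- relative risks for fever "after Visit 1 and Visit 2 separately will also be calculated";
- the count of tests, "There are two separate statistical tests being performed at the alpha 0.05 level".

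Protocol 6.2.3 has a matching sentence without the 1/0 labels, "Fever on day 1 and/or day 2 after either visit will be counted as positive for this analysis". It also compares proportions by visit, but describes the relative risk as being for the "occurrence of any fever on day 1 and/or day 2 after Visit 1 and/or Visit 2 will also be calculated".

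**The concern.** The SO 1 coding sentence in SAP 8.2 a) matches, word for word, the one for the primary objective in SAP 8.1. There it unambiguously means the union of the two visits. It is the only sentence in the SO 1 paragraph that says which children score 1, and coding sentences are what a programmer implements. A child with fever only after Visit 2 should score 0 on SOM 1.1, yet scores 1 under the literal rule. Protocol 6.2.3 adds to the doubt by giving the SO 1 relative risk in the primary endpoint's terms.

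SO 1 has a real purpose. Protocol 1.2 asks whether giving influenza vaccine separately reduces fever or only spreads it over two occasions, and the per-visit comparison bears directly on that. If both tests were run on the composite, they would repeat the primary result under two other labels, and the per-visit relative risks would be lost.

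**Working it through.** **The plan's own figure.** SAP 4.2 gives 36% (simultaneous) and 18% (sequential) for the composite, 126 per group, two-sided alpha 0.05 and 90% power.

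- Retained sample: 280 × 0.9 = 252, or 126 per group.
- Mean proportion 0.27. Standard error under the null: √(2 × 0.27 × 0.73 / 126) = 0.0559. Under the alternative: √((0.36 × 0.64 + 0.18 × 0.82) / 126) = 0.0548.
- z = (0.18 − 1.96 × 0.0559) / 0.0548 = 1.28, so power is 90.1%.

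The stated 90% reproduces. It belongs to POM 1.1. The documents give no sample size or power for SO 1, so no stated figure depends on the SO 1 sentence.

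**The two readings against the text.**

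| Text | Sentence means the union of visits | Sentence means the visit being analysed |
|---|---|---|
| SOM 1.1 and SOM 1.2 (Protocol 2.1, SAP 3.2) | Contradicts both | Agrees |
| SO 1 objective: visits separately | Contradicts | Agrees |
| Proportions compared visit by visit (SAP 8.2 a, Protocol 6.2.3) | No per-visit proportion exists | Agrees |
| Relative risk for each visit (SAP 8.2 a) | Contradicts | Agrees |
| Two tests (SAP 8.2 a) | One variable, hence one test | Agrees |
| Relative-risk wording in Protocol 6.2.3 | Agrees | Contradicts |

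The plan also says so when it wants a combined result: SO 2 is to be analysed by visit and combined, whereas SO 1 is by visit only.

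**What literal coding would produce.** Both SO 1 comparisons would be 0.36 / 0.18 = 2.00, with 126 × 0.36 = 45.4 and 126 × 0.18 = 22.7 children. They would match each other and the primary result exactly, so the error would be plain in the first table.

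**How different the per-visit results might be (illustration only).** Keep the composite rates. Assume independent visits and 7.5% fever after influenza vaccine alone (the earlier observational study described in Protocol 1.1). Let b be background fever after Visit 2 in the simultaneous group; b is an assumption, not given in the documents.

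- Sequential, Visit 1: 1 − 0.82 / 0.925 = 11.4%. Visit 2: 7.5%.
- Simultaneous, Visit 1: 1 − 0.64 / (1 − b). Visit 2: b.

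| b | Visit 1, simultaneous | Visit 1 relative risk | Visit 2 relative risk (b / 0.075) |
|---|---|---|---|
| 0 | 36.0% | 3.17 | 0 |
| 5% | 32.6% | 2.87 | 0.67 |
| 7.5% | 30.8% | 2.71 | 1.00 |
| 10% | 28.9% | 2.55 | 1.33 |

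The per-visit and composite endpoints therefore answer different questions. The table shows what a misreading would lose, not that one is likely, and the direction at Visit 2 turns on the assumed b.

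**The case for a change.** The strongest case for a change is that reading the sentence as referring to the visit under analysis gives identical words two meanings in adjacent sections, with nothing to mark the switch. A final SAP should not rely on the programmer to notice, and the edit is cheap. Exploratory Objective 3 reports fever grades by visit, but it uses a mean-score test and specifies no relative risk for any fever, so it would not replace SO 1.

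Some of this stands. The wording is careless, the protocol and SAP do differ on the relative risk, and Exploratory Objective 3 is no substitute. What does not stand is that the analysis is left undetermined. The switch is marked by the endpoint definitions, the comparison sentence, the relative-risk sentence and the count of tests. On the relative risk, the SAP is the document that specifies the analysis, and it already has the per-visit form.

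A rewrite is also not automatically harmless. Defining each indicator as 1 for fever after that visit and 0 otherwise would explicitly score as afebrile any intent-to-treat child with no Visit 2 temperatures, because SAP 6.1 requires only a study vaccine at Visit 1. The present text is itself loose about missing readings (no fever reported counts as 0), but that is a separate question and a wording repair should not settle it in passing.

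**Conclusion.** The concern does not call for a change. The SO 1 sentence is a clerical carry-over from the primary objective, and the protocol's relative-risk phrase is of the same kind. An analyst following SAP 8.2 a) with the SAP 3.2 definitions would build one indicator per visit and run two tests, as intended. Aligning the words would change no planned result. The primary analysis, the 280 enrolled, the 90% power and the alpha level do not involve this sentence.

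The conclusion rests on the SAP's explicit per-visit statements governing the analysis, not on the illustrative relative risks, which depend on independent visits, an external 7.5% rate and an assumed background rate. If the documents are reopened for other reasons, saying that fever is counted after the visit concerned would be a harmless tidy-up.

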8.3 Exploratory Objectives

There are eight exploratory objectives for this study.

- a) The first exploratory objective (EO 1) is to compare the height and duration of fever on day 1 and/or day 2 after Visit 1 and Visit 2 (separately and combined) in the simultaneous versus sequential group. The average peak temperature of each child with fever during the risk window of days 1 and 2 (temperature $\geq 38.0^{\circ}\text{C}$ or $\geq 100.4^{\circ}\text{F}$) and the total number of fever degree-days (temperature $\geq 38.0^{\circ}\text{C}$ or $\geq 100.4^{\circ}\text{F}$) following Visit 1, Visit 2 and Visit 1 and 2 combined will be presented by simultaneous and sequential vaccination groups. These six comparisons will be made using a Mann-Whitney U/Wilcoxon rank-sum test.
- b) The second exploratory objective (EO 2) is to compare the use of antipyretics for fever on day 1 and/or day 2 after Visit 1 and Visit 2 (separately and combined) in the simultaneous versus sequential group. The use of antipyretics for fever on day 1 and/or day 2 after Visit 1 and Visit 2 (separately and combined) will be presented for the simultaneous versus sequential group in tables. These three proportions of children with antipyretic use on day 1 and/or day 2 following Visit 1, Visit 2, and Visit 1 and Visit 2 combined will be compared using a Mantel-Haenszal statistic in a stratified analysis by site between the simultaneous and sequential vaccination groups.
- c) The third exploratory objective (EO 3) is to describe and compare the level of severity of fever following Visit 1 and Visit 2 separately, in the simultaneous versus sequential group. Fever will also be assessed at different levels of severity (Grades 1, 2, and 3) on day 1 and/or day 2 and days 3-8 following Visit 1 and separately for Visit 2. The grade levels are defined in Table 2.

Temporal Artery Temperature	None	Mild (Grade 1)	Moderate (Grade 2)	Severe (Grade 3)
°C	≤ 37.9	$\geq 38.0 - \leq 38.5$	$\geq 38.6 - \leq 39.5$	≥ 39.6
°F	≤ 100.3	$\geq 100.4 - \leq 101.3$	$\geq 101.4 - \leq 103.1$	≥ 103.2

There will be six (day 1 and/or day 2, days 3-8, and days 1-8 following Visit 1 and separately for Visit 2) statistical comparisons performed at the alpha 0.05 level. These group comparisons will be made using a Mantel-Haenszel statistic (row mean scores difference with standardized midranks scores [modified ridit scores]) in a stratified analysis by site to control for the randomization blocks.

- d) The fourth exploratory objective (EO 4) is to compare the proportions of children with fever on at least one day during days 3-8 after Visit 1 and Visit 2 (separately and combined) in the simultaneous versus sequential group. This information is captured on the memory aid form in the REDCap database. There will be three statistical comparisons performed at the alpha 0.05 level. These group comparisons will be made using a Mantel-Haenszel statistic in a stratified analysis by site to control for the randomization blocks.
- e) The fifth exploratory objective (EO 5) is to compare the clinical importance of fever occurring on at least one day during days 3-8 after Visit 1 and Visit 2 (separately and combined) in the simultaneous versus sequential group. Clinical importance is assessed based on severity of fever, duration of fever, and medical care utilization for fever. This information is captured on the memory aid form in the REDCap database.

1. Severity of fever: To evaluate the severity of fever, the proportions of children with moderate/severe fever (GRADE 2 and/or 3 see Table 2 above) on at least one day during days 3-8 following Visit 1, Visit 2, and Visit 1 and Visit 2 combined will be presented in a tabular format. This group comparison will be made using a Mantel-Haenszel statistic in a stratified analysis by site to control for the randomization blocks.
2. Duration of fever: To evaluate the duration of fever, the average number of consecutive days of fever (temperature $\geq 38.0^{\circ}\text{C}$ or $\geq 100.4^{\circ}\text{F}$) per subject for fever starting on day 3-8 following Visit 1, Visit 2, and Visit 1 and Visit 2 combined will be calculated. A fever starting on day 3-8 could continue through day 8. The mean duration of any fever will be presented in days for children with fever that began on days 3-8 after Visit 1 and Visit 2 (separately and combined). Each consecutive day of fever on the memory aid will be counted per child per visit. Thus, a child could contribute a maximum of 6 days per study visit, should a fever be reported at each day on the memory aid. The longest duration of any fever occurring for a child will be counted for that child. e.g. If a child has fever on days 3 and 4, no fever on day 5, and fever occurring on days 6, 7, and 8 the duration of fever will be counted as 3 days for that child.

There will be three statistical comparisons performed (mean duration of any fever starting on days 3-8 following Visit 1, Visit 2, and Visit 1 and Visit 2 combined) at the alpha 0.05 level. These group comparisons will be made using a Mann-Whitney U/Wilcoxon rank-sum test.

3. Medical care utilization for fever: The proportion of children with medical care utilization determined by report on the diary (telephone call, medical office visit, emergency department visit, or hospital admission) for fever on at least one

day during days 3-8 following Visit 1, Visit 2, and Visit 1 and Visit 2 combined, will be presented in tables or the simultaneous versus sequential group. There will be three statistical comparisons performed. These group comparisons will be made using a Mantel-Haenszal statistic in a stratified analysis by site to control for the randomization blocks.

- f) The sixth exploratory objective (EO 6) is to describe and compare the occurrence of solicited systemic adverse events (excluding fever) on days 1-8 after Visit 1 and Visit 2 in the simultaneous versus sequential group. Table 3 below lists the solicited adverse events to be collected.

Table 3: Solicited Systemic Adverse Events				
	None	Mild (Grade 1)	Moderate (Grade 2)	Severe (Grade 3)
Fussiness or Irritability	None	Less playful than usual but not requiring more attention and able to console	Requiring increased attention but able to console	Unable to console
Change in eating habits	None	Eating less than normal for 1 to 2 feeds/meals	Missed 1 or 2 feeds/meals completely	Refuses ≥ 3 feeds/meals or refuses most feeds/meal
Drowsiness or Sleepiness	None	Drowsiness but still interested in surroundings and did not miss feed or meal	Not interested in surroundings or did not wake up for a feed or meal	Sleeps most of the time or difficult to wake up

Listings of all solicited adverse events will be produced showing vaccination group, date of onset, date of resolution, and highest grade level. The frequency and percentage of the highest grade level for participants will be presented by each of the three solicited adverse events. There will be three statistical comparisons made using a Mantel-Haenszal statistic (row mean scores difference with standardized midranks scores [modified ridit scores]) in a stratified analysis by site to control for the randomization blocks.

- g) The seventh exploratory objective (EO 7) is to describe and compare the occurrence of febrile seizure and/or serious adverse events during the period of enrollment (i.e., from Visit 1 through 8 days after Visit 2) in the simultaneous versus sequential group. Listings of all febrile seizure and/or serious adverse events will be produced showing vaccination group, description, relatedness, date of onset, date of resolution, and SAE category. The frequency of the occurrence of febrile seizure and/or serious adverse events by vaccination group will be compared using a Fisher's Exact test because the expected number of events is very low (i.e., small cell counts).
- h) The eighth exploratory objective (EO 8) is to describe and compare the perceptions among parents/ legally authorized representatives (LARs) of the simultaneous versus sequential schedule experience. Summary tables of acceptability will be produced by vaccination group. Likert scale questions will be compared between the vaccination groups using a Mantel-Haenszal statistic (row mean scores difference with standardized midranks scores [modified ridit scores]) in a stratified analysis by site to control for the randomization blocks.

No adjustments will be made to the alpha level (two-sided $\alpha=0.05$) for these exploratory analyses.

